## 7 Study Interventions

Study vaccinations will comprise 1 intramuscular (IM) injection (Day 1) of 0.5 mL injection volume with a total dose of 5 µg recombinant rS antigen with 50 µg Matrix M adjuvant. Vaccine will be administered as an open-label material.

Vaccine	Baseline Serostatus	Number of Doses	Number of Participants	Dose (antigen/Matrix-M adjuvant)
Ancestral strain NVX-CoV2373	Previously vaccinated	1	100-150	5 µg / 50 µg
Updated Novavax COVID-19 Vaccine based on recent variant(s)	Previously vaccinated	1	100-150	5 µg / 50 µg

### 7.1 Description of Products

#### 7.1.1 NVX-CoV2373 Ancestral Strain

##### 7.1.1.1 Formulation, Storage, Preparation, and Handling

NVX-CoV2373 ancestral strain SARS-CoV-2 rS vaccine will be supplied as a solution for preparation for injection of SARS-CoV-2 rS at a concentration of 10 µg/mL and Matrix-M adjuvant at a concentration of 100 µg/mL.

NVX-CoV2373 should be stored at 2 to 8°C in a secured location. DO NOT FREEZE. The study site will maintain a temperature log to establish a record of compliance with storage conditions.

Further details on the trial vaccine can be found in the SARS-CoV-2 rS IB and a description of its preparation can be found in the Pharmacy Manual.

##### 7.1.1.2 Packaging and Labeling

The Sponsor will provide adequate quantities and appropriate labelling of SARS-CoV-2 rS with Matrix-M adjuvant and Syneos Health will ensure distribution to the study sites from a designated depot. The clinical unit pharmacy or equivalent will prepare the clinical trial materials. Detailed instructions for the handling of trial vaccine vials will be provided in a separate Pharmacy Manual.

##### 7.1.1.3 Dosing and Administration

The vaccine should be drawn into a syringe on the day of administration by a qualified member of study site personnel and administered according to standard practice by qualified study site personnel as described in the Pharmacy Manual.

### **7.1.2 Updated Novavax COVID-19 Vaccine Based on Recent Variant(s)**

#### **7.1.2.1 Formulation, Storage, Preparation, and Handling**

The Updated Novavax COVID-19 vaccine will be supplied as a solution for preparation for injection of SARS-CoV-2 rS antigen at a concentration of 10 µg/mL and Matrix-M adjuvant at a concentration of 100 µg/mL.

The Updated Novavax COVID-19 vaccine should be stored at 2 to 8°C in a secured location. DO NOT FREEZE. The study site will maintain a temperature log to establish a record of compliance with storage conditions. Description of its preparation can be found in the Pharmacy Manual.

#### **7.1.2.2 Packaging and Labeling**

The Sponsor will provide adequate quantities and appropriate labelling of SARS-CoV-2 rS with Matrix-M adjuvant and Syneos Health will ensure distribution to the study sites from a designated depot. The clinical unit pharmacy or equivalent will prepare the clinical trial materials. Detailed instructions for the handling of trial vaccine vials will be provided in a separate Pharmacy Manual.

#### **7.1.2.3 Dosing and Administration**

The vaccine should be drawn into a syringe on the day of administration by a qualified member of study site personnel, and the vaccine should be administered according to standard practice by qualified study site personnel as described in the Pharmacy Manual.

## **7.2 Treatment Assignment and Bias Minimization**

### **7.2.1 Treatment Allocation**

As this is an open-label trial, a log of the participant ID number with the treatment vial administered will be completed at the site and will be held by Syneos Health during the study.

### **7.2.2 Assessment and Verification of Compliance**

Study vaccine should be administered in the clinical unit under direct observation of clinic personnel and recorded in the eCRF. The vial number of the vaccine will be recorded for each study participant. Clinic personnel will confirm that the participant has received the entire dose.

The location (right or left arm, or other location if required), if the full dose was administered, date, and timing of all doses of study vaccine will be recorded in the participants' eCRF. If a participant is not administered study vaccine, the reason for the missed dose will be recorded.

## **7.3 Prior and Concomitant Therapies**

Administration of medications, therapies, or vaccines will be recorded in the concomitant medication eCRF. Prior medications include recent ( $\leq$  90 days) and current medications and non-COVID-19 vaccinations. Concomitant medications will include all medications (including vaccines) taken by the participant from the time of signing the ICF through Day 29 (or through the early termination visit if prior to that time). Prescription and OTC drugs will be included. Do

not record herbals, vitamins, and supplements. After Day 29, concomitant medications that may have caused or are being used to treat an AE should be recorded.

Receipt of all COVID-19 vaccines prior to screening should be recorded in the Vaccine History eCRF. Site staff will record the date(s) and brand of the SARS-CoV-2 vaccine received. Any COVID-19 vaccine received from Day 30 until EOS should be recorded.

### **7.3.1 Prohibited Therapies**

The following therapies are prohibited within the specified timeframes of study conduct:

- Any COVID-19 vaccines during the course of the study.
- Seasonal influenza vaccine may not be administered < 4 days before or < 7 days after the study vaccine.
- All other vaccines, except rabies vaccine (if medically indicated),  $\leq$  90 days before enrollment until Day 29.
- Investigational product (drug/biologic/device) from time of enrollment until after the last study visit.
- Immunoglobulins, monoclonal antibodies, blood products, or any therapy that causes clinically significant immunosuppression within 90 days of study vaccination until the EOS visit. Similarly, rabies immune globulin should be administered if medically indicated.

## 8 Safety assessments

The timing and frequency of all safety assessments are listed in the SOE ([Table 1](#)).

Solicited (reactogenicity) and unsolicited AEs will be graded for severity using the provided criteria ([Appendix 3](#)). Recording of solicited and unsolicited AEs will be conducted by EDC. AESIs, including PIMMCs, myocarditis and/or pericarditis (see [Table 3](#)), and complications specific to COVID-19, will also be monitored (see [Appendix 2](#) for details).

A central Cardiac Adjudication Committee has been established to adjudicate suspected myocarditis and/or pericarditis cases in the clinical development plan of NVX-CoV2373. Outcomes of the adjudications will be communicated to the Sponsor.

### 8.1 Definitions

- **Adverse event** – An AE is any untoward medical occurrence associated with the use of an intervention in humans whether or not it is considered intervention-related. Any abnormal laboratory test results or other safety assessments (eg, physical examination, vital signs measurements) that are clinically significant in the medical and scientific judgment of the investigator (ie, not related to progression of underlying disease) will be considered AEs. An exacerbation of a chronic or intermittent pre-existing condition, including either an increase in frequency and/or intensity, will be considered an AE.
- **Serious adverse event (SAE)** – An event is considered “serious” if, in the view of either the Investigator or Sponsor, it results in any of the following outcomes:
  - Death
  - A life-threatening AE (an event is considered “life-threatening” if, in the view of either the investigator or Sponsor, its occurrence places the patient or participant at immediate risk of death. It does not include an AE or suspected adverse reaction (AR) that, had it occurred in a more severe form, might have caused death.)
  - Inpatient hospitalization or prolongation of existing hospitalization. In general, hospitalization signifies that the participant has been detained, usually involving an overnight stay, at the hospital or emergency ward for observation and/or treatment that would not have been appropriate in the physician’s office or outpatient setting. Hospitalization for elective treatment of a pre-existing condition that did not worsen from baseline is not considered an SAE.
  - A persistent or significant incapacity or substantial disruption of the ability to conduct normal life functions
  - A congenital anomaly/birth defect
  - Important medical events that may not result in death, be life-threatening, or require hospitalization may be considered serious when, based upon appropriate medical judgment, they may jeopardize the patient or participant and may require medical or surgical intervention to prevent one of the outcomes listed in this definition. Examples of such medical events include allergic bronchospasm requiring intensive treatment in an emergency room (ER) or at home, blood dyscrasias or convulsions that do not result in inpatient hospitalization, or the development of drug dependency or drug abuse.

- **Causality or relatedness** – For each AE/SAE, the Investigator must document in the medical notes that he/she has reviewed the AE/SAE and has provided an assessment of causality as follows.
  - Not Related: There is no reasonable possibility of relationship to study vaccine. The AE does not follow a reasonable temporal sequence from administration of study vaccine or can be reasonably explained by the participant's clinical state or other factors (eg, concurrent diseases, and concomitant medications).
  - Related: There is a reasonable possibility of relationship to study vaccine. The AE follows a reasonable temporal sequence from administration of study vaccine and cannot be reasonably explained by the participant's clinical state or other factors (eg, concurrent diseases or concomitant medications), represents a known reaction to study vaccine or other vaccines in its class, is consistent with the known pharmacological properties of the study vaccine, and/or resolves with discontinuation of the study vaccine (and/or recurs with re-challenge, if applicable).
- **Adverse reaction** – An AR is any AE caused by the investigational product.
- **Suspected adverse reaction (SAR)** – An SAR is any AE for which there is a reasonable possibility that the drug caused the AE. For the purposes of IND safety reporting, “reasonable possibility” means there is evidence to suggest a causal relationship between the drug and the AE. SAR implies a lesser degree of certainty about causality than AR.
- **Unexpected** – An event is considered unexpected if it is not listed in the IB, is not listed at the specificity or severity that has been observed, or, if an IB is not required or available, is not consistent with the risk information described in the General Investigational Plan or elsewhere in the IND. Unexpected also refers to events that are mentioned in the IB as occurring with a class of drugs or as anticipated from the pharmacological properties of the drug but are not specifically mentioned as occurring with the particular drug under investigation.
- **Severity or intensity** – The severity (or intensity) of an AE/SAE refers to the extent to which it affects the participant's daily activities and will be classified as mild, moderate, or severe using the following criteria:
  - Mild: These events require minimal or no treatment and do not interfere with the participant's daily activities.
  - Moderate: These events result in a low level of inconvenience or require minor therapeutic measures. Moderate events may cause some interference with normal functioning.
  - Severe: These events interrupt a participant's usual daily activity and may require systemic drug therapy or other treatment. Severe events are usually incapacitating.

If the severity of an AE/SAE changes, the most intense severity should be reported. An AE/SAE characterized as intermittent does not require documentation of the onset and duration of each episode. Grading criteria for specific AEs are provided in [Appendix 2](#).

### 8.1.1 Documenting Adverse Events

At every study visit and phone call, participants will be asked to report any medically related changes in their well-being. They will also be asked if they have been hospitalized, had any

accidents, used any new medications that may have caused or were used to treat an adverse event, or changed concomitant medication regimens (both prescription and OTC medications).

In addition to participant observations, AEs will be documented from any data collected on the AE page of the eCRF or other documents that are relevant to participant safety.

Care will be taken not to introduce bias when detecting AEs, MAAEs, and SAEs. Open-ended and non-leading verbal questioning of the participant is the preferred method to enquire about AE occurrences. AESIs will be inquired about according to the specific diseases listed in [Appendix 2](#).

When an AE/SAE occurs, it is the responsibility of the investigator to review all available documentation (eg, hospital progress notes, laboratory reports, and diagnostics reports) related to the event. The investigator will then record all relevant AE/SAE information in the eCRF.

It is not acceptable for the investigator to send photocopies of the participant's medical records in lieu of completion of the AE/SAE eCRF page. There may be instances when copies of medical records for certain cases are requested. In this case, all participant identifiers, with the exception of the participant number, will be redacted on the copies of the medical records before submission. The investigator will attempt to establish a diagnosis of the event based on signs, symptoms, and/or other clinical information. Whenever possible, the diagnosis (not the individual signs/symptoms) will be documented as the AE/SAE.

The following variables will be recorded for each AE: verbatim/AE description and date for AE start and stop, severity, seriousness, causality, any other action taken, and the outcome. A new AE must be recorded if the severity of the AE changes.

Should an SAE have an outcome of death, the report should contain a comment regarding the coinvolvement of progression of disease, if appropriate, and should assign main and contributory causes of death.

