9. Reactogenicity (solicited adverse events related to vaccination) will be recorded by participants via diary on Days 1-7. The diary will be collected from the participant at the Day 8 visit and will be used to populate reactogenicity data in EDC. Should any reactogenicity event extend beyond 7 days after vaccination (toxicity grade  $\geq$ 1), then it will be recorded as an AE with the same start date as the reactogenicity event and followed to resolution.
10. All MAAEs and all AESIs (including potential immune-mediated medical conditions [PIMMCs] and myocarditis or pericarditis will be recorded. See [Table 3](#) for symptoms of myocarditis or pericarditis and [Table 4](#) for instructions for follow-up.
11. MAAEs attributed to study vaccine and all AESIs (including PIMMCs and myocarditis or pericarditis) will be recorded. See [Table 3](#) for symptoms of myocarditis or pericarditis and [Table 4](#) for instructions for follow-up.
12. EOS form will be completed for all participants, including participants who are terminated early.

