#### **6.1.3 Day 8 Visit**

The following activities will occur at the Day 8 visit:

- The diary that participants use to record reactogenicity data between Days 1 and 7 will be reviewed with the participants and collected so that site personnel can record the information by electronic data capture (EDC).
- Recording of unsolicited AEs, SAEs, MAAEs, and AESIs (including PIMMCs and myocarditis or pericarditis). See [Table 3](#) for symptoms of myocarditis or pericarditis and [Table 4](#) for instructions for follow-up.

**NOTE:** Should any reactogenicity event extend beyond 7 days after vaccination (toxicity grade  $\geq 1$ ), then it will be recorded as an AE with the same start date as the reactogenicity event and followed to resolution.

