#### 8.1.4.4 Reactogenicity Symptoms

On the day of vaccination, participants will remain in clinic (or under observation) for at least 15 minutes to be observed for any immediate reaction. Injection site specific local and general systemic reactogenicity reactions including start and stop dates will be recorded following vaccination. Any immediate reaction will be recorded as an AE on day of vaccination.

Participants will utilize their diary to record reactogenicity for the 7 days following vaccination. All participants will record reactogenicity starting on the same day of the vaccination and for a total of 7 days. Should any reactogenicity event extend beyond 7 days after vaccination (toxicity Grade  $\geq 1$ ), then it will be recorded as an AE with a start date that matches Day 8 of the reactogenicity event and followed to resolution per FDA guidelines for AE capture. The toxicity grading scale implemented in the diary is included in [Appendix 3](#).

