### **9.3.3 Safety Analyses**

To describe the overall safety of ancestral strain and updated (if administered) Novavax vaccine(s) administered as a second (or subsequent) booster following licensed mRNA vaccines and a first ancestral strain Novavax vaccine booster, the secondary endpoints of safety data include solicited AEs in the 7 days following study vaccination and MAAEs, AESIs (including myocarditis and/or pericarditis), and SAEs throughout the study. All safety analyses will be descriptive and conducted using the Safety Analysis Set.

All local/systemic solicited (reactogenicity) AEs within the post-vaccination window (Days 1-7) by the verbatim terms, and by severity (mild, moderate, severe) using the maximal severity observed for the specific symptom post-vaccination will be summarized for each study vaccine group.

Unsolicited MAAEs, AESIs (including myocarditis and/or pericarditis), and SAEs throughout the study will be summarized by the study vaccine group and by SOC and PT using MedDRA terms, as well as by severity and relationship to the study vaccine to present the number and percentage with its corresponding exact 95% CIs using Clopper-Pearson method. For multiple occurrences of an AE in the same participant, a participant will be counted only once within an SOC or a PT, using the most severe occurrence and closest reported relationship for the summarization by severity or relationship to the study vaccine, respectively. The duration of MAAEs, AESIs, and SAEs through Day 181 will also be summarized.

A by-participant listing of MAAEs, AESIs, and SAEs throughout the study will also be provided.

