7.3.2 Unsolicited Adverse Events

A MAAE is defined as an AE that leads to an unscheduled visit to a healthcare practitioner. All MAAEs will be reported from the time of study vaccination through Day 29. After Day 29, MAAEs attributed to study vaccine will be captured until EOS. AESIs include PIMMCs, myocarditis and/or pericarditis ([Table 11](#) in Appendix 4), and complications specific to COVID-19 ([Table 9](#) in Appendix 2). SAE is an event considered “serious” if, in the view of either the Investigator or Sponsor, it results in any of the outcomes listed in Section 8.1 of the Study 312 Protocol.

Unsolicited MAAEs through Day 29, and MAAEs attributed to study vaccine/AESIs/SAEs throughout the study will be summarized by the study vaccine group and by SOC/PT using the latest version of MedDRA, as well as by severity (Mild, Moderate, Severe) and relationship (not related, related) to the study vaccine to present the number and percentage with its corresponding exact 95% CIs using Clopper-Pearson method. For multiple occurrences of an AE in the same participant, a participant will be counted only once within an SOC or a PT, using the most severe occurrence and closest reported relationship for the summarization by severity or relationship to the study vaccine, respectively.

The duration of MAAEs through Day 29, MAAEs attributed to study vaccine after Day 29 until EoS, AESIs and SAEs throughout the study will be summarized and their corresponding by-participant listings will also be provided.

The following summaries of all unsolicited AEs will be presented by the study vaccine group as the part of safety stated as the secondary endpoints:

- Overall summary of all unsolicited TEAEs (Days 1 – 29)
- Summary of all unsolicited TEAEs by MedDRA SOC/PT and severity (Days 1 – 29)
- Summary of all unsolicited TEAEs by MedDRA SOC/PT and relationship to the study vaccine (Days 1 – 29)
- Summary of MAAEs by MedDRA SOC/PT and severity (Days 1 – 29)
- Summary of MAAEs by MedDRA SOC/PT and relationship to the study vaccine (Days 1 – 29)

- Summary of MAAEs attributed to study vaccine by MedDRA SOC/PT and severity (Days 1 – 29) and (Days 1 – 181)
- Summary of AESIs (including PIMMCs, myocarditis or pericarditis, and complications to COVID-19) by MedDRA SOC/PT and severity (Days 1 – 29) and (Days 1 – 181)

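### Conflicting AE recording rules on severity change and on the start date of prolonged reactions leave the MAAE, AESI and SAE duration summaries dependent on which rule a site follows

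*Protocol*

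**What the plan says.** **Change of severity.** Protocol 8.1, in its definition of severity: "If the severity of an AE/SAE changes, the most intense severity should be reported". The next sentence there waives separate onset and duration for each episode of an intermittent event. Protocol 8.1.1, in its list of what is recorded for each AE (start and stop dates, severity and so on): "A new AE must be recorded if the severity of the AE changes".

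**Start date of a reaction that continues past Day 7.** Protocol 6.1.3 has it "recorded as an AE with the same start date as the reactogenicity event and followed to resolution". Protocol Table 1 footnote 9 and SAP Table 7 footnote 9 say the same. Protocol 8.1.4.4 instead has it "recorded as an AE with a start date that matches Day 8 of the reactogenicity event".

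**Use of the data.** Protocol Table 2 and SAP Table 3 list incidence, duration, severity and relationship of MAAEs and AESIs as a secondary safety endpoint. For SAEs the endpoint is incidence and relationship only, but Protocol 9.3.3 adds: "The duration of MAAEs, AESIs, and SAEs through Day 181 will also be summarized". The text of SAP 7.3.2 also plans duration summaries for all three classes. SAP 11.5 covers partial dates, missing severity and missing relationship. It says nothing about one event held as several records.

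**The concern.** A site cannot follow both instructions in either pair. If one site opens a new AE whenever severity changes and another keeps a single record, the same illness contributes different numbers and lengths of records to the duration tables. The output would not show which rule had been used. Duration of MAAEs and AESIs is a stated endpoint, so this reaches a planned result. The start-date conflict puts the onset of the same prolonged reaction on different days of the AE page. Some severity tables could also differ, because a split record can fall in a different time window from the record it came from.

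**Working it through.** **Counting convention.** Duration = end day − start day + 1. This reproduces all three worked examples in SAP 7.3.1:
- Method 1, fever on Days 2, 3 and 5: count = 3.
- Method 2, same days: 5 − 2 + 1 = 4.
- Method 3, diary Days 3, 4 and 6 with a linked AE ending Day 8: 8 − 3 + 1 = 6.

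The cases below are illustrations. The documents give no frequency of severity-changing MAAEs or AESIs.

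**Step 1. Severity split and MAAE/AESI/SAE duration.**
- Mild for 6 days, then moderate for 4. One record: 6 + 4 = 10 days. Two records: (6 + 4)/2 = 5 days on average.
- Moderate Days 10–14, severe Days 15–20, mild Days 21–25. One record: 25 − 10 + 1 = 16 days. Split: 5, 6 and 5 days, mean 16/3 = 5.3. The participant's worst severity is severe either way.

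**Step 2. Start date.** The two rules differ by 8 − onset day, so by 1 day (onset Day 7) to 7 days (onset Day 1).

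| Reaction | AE record, reaction's start date | AE record, Day 8 start | SAP method 3 |
|---|---|---|---|
| SAP example, Day 3 to Day 8 | 6 days | 1 day | 6 days under both |
| Fatigue, Day 2 to Day 12 | 12 − 2 + 1 = 11 days | 12 − 8 + 1 = 5 days | 11 days under both |

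Method 3 starts at the first diary day and ends with the linked AE, so the AE-page start date does not enter. That date matters for the AE-page onset, for listings, and for the duration of any prolonged reaction that is also an MAAE or SAE and is measured from its AE record. It moves nothing in or out of the Days 1–29 tables, because Days 1–7 and Day 8 all fall inside that window.

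**Step 3. Severity split of a prolonged reaction.** Take diary onset Day 3, then an AE of grade 2 on Days 8–9 and grade 1 on Days 10–12. With one linked record, method 3 gives 12 − 3 + 1 = 10 days. If only the first split record is linked, it gives 9 − 3 + 1 = 7 days. So the severity conflict can reach this duration, through the end date.

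**Step 4. Where severity can differ.** SAP 7.3.2 counts a participant once per SOC or PT at the worst severity. That absorbs splitting as long as all parts are collected and fall in the same window. Three situations escape it:
- *AESI, mild from Day 25 and severe from Day 35.* If records enter a table by onset date (an assumption; the SAP does not say), one record is severe in the Days 1–29 table. Split records are mild there. Both give severe in the Days 1–181 table.
- *MAAE not attributed to vaccine that worsens after Day 29.* Protocol 8.1.4.3 then collects only vaccine-attributed MAAEs, so a new record for the worsening falls outside collection. A single record might be updated to the higher severity.
- *Prolonged reaction in the SAP 7.3.1 table of severity beyond 7 days.* A record dated from reaction onset at worst severity can carry a Days 1–7 peak. A record starting on Day 8 would not.

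**The case against.** The strongest reply is that this is a wording inconsistency in a descriptive safety analysis, and that the SAP already contains most of the consequences. Much of that stands.

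- A reader might infer that durations of prolonged reactions depend on the start-date conflict. They do not under SAP method 3, as Step 2 shows.
- A reader might infer that splitting inflates the incidence tables. SAP 7.3.2 counts each participant once per SOC or PT, so the number and percentage of participants do not rise.
- A reader might infer that worsening after Day 29 is systematically lost under 8.1.1. AESIs and SAEs are collected to end of study and tabulated for Days 1–181, so their worst severity survives there. For an MAAE not attributed to vaccine, the phone calls after Day 29 do not ask for it. Capture of the worsening is therefore not assured under 8.1 either, and a difference between the rules is possible but not certain.
- Protocol 8.1 does not literally order a single record; that is an inference. It is a strong one. Choosing the most intense severity presupposes one event with one severity, and the waiver for intermittent episodes points the same way. The worst-severity counting in SAP 7.3.2 works with one record or several, so it does not settle the question.

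The reply does not answer the duration summaries. Nothing in either document tells the programmer to rejoin records before computing MAAE, AESI or SAE duration.

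**Conclusion.** Both contradictions are in current operative text and should be reconciled. The firm consequence is that the MAAE, AESI and SAE duration summaries are not uniquely defined. In the illustrations a 10-day event becomes two averaging 5 days, and a 16-day event becomes three averaging 5.3. How often this would occur cannot be stated, because the documents do not give the frequency of severity changes.

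Severity is exposed only in the three situations of Step 4. The first rests on tables assigning records by onset date; the second rests on a site updating a single record after Day 29. The start-date conflict is worth 1 to 7 days per event on the AE page, in listings, and for a prolonged reaction that is also an MAAE or SAE.

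The documents do not support anything wider. Participant-level incidence is unchanged, no immunogenicity endpoint or hypothesis is touched, and all safety analyses are descriptive. This should be corrected, but it does not threaten the trial's main conclusions.

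**What to change.** 1. Protocol 8.1 and 8.1.1: keep one AE record from onset to resolution at maximum severity, and delete the sentence in 8.1.1 that calls for a new AE.
2. Protocol 8.1.4.4: give a reaction continuing past Day 7 the reaction's own start date, as in Table 1 footnote 9, 6.1.3 and SAP Table 7 footnote 9.
3. SAP 7.3.2: state that records already split are joined, for duration and maximum severity, only when they are contiguous and confirmed by linkage or site query to be the same event. A matching preferred term alone is not enough, since it could merge distinct episodes.

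Diary-linked AEs should stay in the unsolicited tables. Removing them would resolve neither contradiction and could drop medically attended or serious events.

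The cost is two protocol sentences, one SAP rule, updated eCRF completion guidance, and queries for records already entered. Joining cannot recover a worsening after Day 29 that was never recorded; only a site query can. The downside is that dates for each severity level within an event are no longer captured separately.
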